2.4.2 Prior, concomitant and post therapies

Medications and significant non-drug therapies started and stopped prior to study treatment, and those taken concomitantly, will be summarized based on SAF. Among the concomitant medications, rescue medications will be summarized based on SAF. The medications and significant non-drug therapies will be classified into “prior”, “concomitant”, “post-treatment” based on the start/end dates. The rescue therapy will be used for analysis as it is reported by the investigator under the subcategory of Rescue Medications/Therapy on the Concomitant Medication, Surgical and Medical Procedures CRF pages. Prior: Any medication and significant non-drug therapy with a start date and end date before Day 1.

Concomitant: Any medication or significant non-drug therapy administered at least once during the duration of the treatment (as defined in [Section 2.4.1](#)). It does not include 7 days after the last dose of iptacopan as in the definition of the on-treatment period for treatment emergent adverse event (TEAE). Medications started prior to first day of study drug intake and continuing after study drug start will be counted as concomitant.

Post-treatment medications will be defined as any medication with start date after the end of treatment (any dose).

A therapy started within 7 days after the last dose of iptacopan is not considered as concomitant although some TEAEs leading to concomitant medications may be reported in that period. The objective of this convention is to avoid reporting as concomitant medication some post treatment therapies targeting the study indication.

Prior, concomitant, post-treatment medications will be summarized according to the Anatomical Therapeutic Chemical (ATC) classification system. More than one ATC class per medication is possible and the medication will be reported under all applicable classes.

Prior, concomitant, post-treatment therapies will be recorded and summarized separately for surgical and medical procedures.

All vaccinations received by patients any time during the study (including core treatment period, extension treatment period) will be tabulated by serogroup/polyvalent and for each period. All vaccinations will also be recorded as prior and/or concomitant medication, as appropriate.

2.5 Analysis of the primary objective

For all efficacy analyses based on laboratory data (e.g. hemoglobin, reticulocytes etc.) addressing primary and secondary objectives, the information obtained from the central lab will be used.

2.5.1 Primary endpoint(s)/Primary estimand(s)

The primary endpoint defines the response as sustained increase in hemoglobin and a participant as a responder if :

- The change from baseline in hemoglobin is ≥ 2 g/dL on three out of four measurements taken at the visits occurring in last six weeks (from Day 126 to Day 168) of the Core treatment period, and
- The participant has not met the criteria for administration of RBC transfusions nor received a transfusion between Day 14 and Day 168.
- The baseline hemoglobin will be the mean of the two measurements taken during screening that confirm the hemoglobin entry criterion in patients who do not receive a transfusion between the first and second confirmatory measurement. In patients who receive a transfusion after the first confirmatory hemoglobin measurement, the baseline will be the first measurement.

Criteria for administration of RBC transfusions

To standardize criteria for administration, transfusion criteria have been established and will apply starting from Day 1 of the study.

Packed-RBC transfusions will be administered to participants in the following cases:

- Hemoglobin level of ≤ 9 g/dL (≤ 8 g/dL for Chinese population) with signs and/or symptoms of sufficient severity to warrant a transfusion
- Hemoglobin of ≤ 7 g/dL (≤ 6 g/dL for Chinese population), regardless of presence of clinical signs and/or symptoms

The transfusions information will be collected on the 'Transfusion-during the study' CRF page.

Handling of intercurrent events of primary estimand

Reaching the protocol established criteria for RBC transfusions will be handled using a composite strategy for primary endpoint.

Intercurrent events stemming from discontinuation of treatment, breakthrough hemolysis events and MAVEs, expected to be reflected in the endpoint, will be handled with a treatment policy strategy.

2.5.2 Statistical hypothesis, model, and method of analysis

2.5.2.1 Summary statistics for the primary variable

All descriptive statistics supportive of the primary variable will be based on non-imputed and observed data. For patients who did not require any RBC transfusion (i.e. not met the criteria for administration of RBC transfusions nor received a transfusion) between Day 14 and Day 168 separate summaries will be presented on the following information:

Number of patients having no-missing hemoglobin data in the in last six weeks (from Day 126 to Day 168), number of patients having an increase in hemoglobin ≥ 2 g/dL from baseline on three out of four measurements taken at the visits occurring in last six weeks (from Day 126 to Day 168) of the Core treatment period.

2.5.2.2 Statistical model for primary variable

The primary analysis of the primary endpoint will be a logistic regression to estimate the response probability. The covariates in logistic regression include sex, age (indicator of age ≥ 45 years), an indicator variable of baseline hemoglobin ≥ 8 g/dL and an indicator of transfusion dependence (i.e. whether the patient had any transfusion in the last 6 months prior to starting study treatment).

This means that the proportion of responders will be derived from the estimated marginal probabilities derived from the model fit as the mean of the individual logistic regression model predictions. The 95% confidence intervals will be derived by the bootstrap method (Steingrímsson et al 2017). Refer to [Section 5.2.2.2](#) for details.

In the case that any of the 2^4 cells (given 4 covariates with 2 categories) have zero responders quasi-complete separation (Lu, 2016) may be observed. Moreover, in some imputed datasets or bootstrap samples, all participants are responders/non-responders, and this case will cause fit failure in logistic regression model.

Theoretically it can be shown that point estimate of the marginal probability from the logistic regression model and the simple response probability without the covariates are the same (Refer to [Section 5.2.2.2](#)). Since bootstrap is used to calculate the confidence interval, the confidence interval is also the same from the estimate from the logistic regression model and the simple proportion. Hence, the only reason why there can be a discrepancy in the results is due to a convergence issue (e.g. when all patients are responders/non-responders, quasi-complete separation issues due to covariates) of the logistic regression. However computation using simple proportion does not lead to such convergence issues and hence provide valid estimates.

The results from protocol specified logistic regression method and 95% CI using bootstrap will be computed. If the logistic regression fails to convergence in at least one of the imputed datasets or the bootstrap samples, then the estimates will be obtained using simple proportion. The 95% CI using simple proportion will also be obtained using the bootstrap method. Refer to [Section 5.2.2.2](#) for details.

The primary analysis of primary endpoint is the assessment of the proportion of patients reaching the status of responder (as defined in [Section 2.5.1](#)). The lower bound of the two-sided 95% confidence interval of the response rate obtained from primary analysis will be compared to a threshold of 15%. Lower bound of the two-sided 95% confidence interval $\geq 15\%$ is sufficient for demonstration that iptacopan improves hematological response in PNH patients with hemolysis and anemia in the absence of transfusions. The derivation of the threshold is explained in [Section 5.2.2.3](#).

2.5.3 Handling of missing values not related to intercurrent event.

For the primary response definitions, RBC transfusion will qualify the participant as a non-responder, hence missing hemoglobin data after meeting the criteria for transfusion or after receiving a transfusion during Day 14 to Day 168 does not impact the primary analysis.

Missing hemoglobin data due to withdrawal from study in the core treatment period in the event that a participant did not have a prior RBC transfusion, will be imputed in a multiple imputation framework based on pattern mixture models. This aims to be consistent with the inclusion of hemoglobin data under the treatment policy strategy following all other intercurrent events. The need for transfusion will then be derived from this imputation with imputed values ≤ 9 g/dL (≤ 8 g/dL for Chinese population) considered sufficient to warrant a transfusion. This means assuming conservatively that all patients with imputed hemoglobin between 9 g/dL and 7 g/dL (between 8 g/dL and 6 g/dL for chinese patients) would have presented symptoms warranting transfusion.

- For participants withdrawing from study after discontinuation of iptacopan, the model implemented will recover a return to pre-treatment levels of Hb. This would be implemented by imputing missing values from a normal distribution with mean and standard deviation derived from all baseline hemoglobin values.
- For participants with intermittent missing data, their missing data will be handled with a missing at random approach and imputed consequently.

The model for imputation will be Markov chain Monte Carlo (MCMC) method and only baseline hemoglobin will be included in the imputation model.

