12.4.7 Supportive analyses

The estimation of proportions described above will be further displayed for subgroup categories defined by previous transfusion dependence, length of time since diagnosis, prior supportive therapy (e.g. steroids, androgens etc.), age categories, sex, and baseline hemoglobin.

Other supportive analyses

Potential impact of a new wave of COVID-19 infections affecting measurements have been minimized through the measures proposed in [Section 8](#). Other impact that at this stage cannot be excluded such as withdrawal from study follow up due to infection which would require dealing with such events as additional intercurrent events. This would define additional estimands, possibly primary and secondary estimands all of which would deal with the COVID-19 related intercurrent events so that inference would still concern treatment effects in a world that is not in the midst of an extraordinary pandemic situation. The methodology for the analyses targeting these estimands and additional sensitivity analyses for cases of missing data due to the impact of COVID-19 infections will be specified in detail in an amendment to the SAP developed in the event of renewed COVID-19 infection waves. Decisions on handling of possible increases in background risks impacting study endpoints will also take into consideration relevant epidemiological information on local incidence of COVID-19 infections.

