2.6 Analysis of secondary endpoints/estimands

2.6.1 Secondary endpoints/secondary estimands

Descriptive statistics and summaries on the secondary endpoints based on FAS will be provided.

2.6.1.1 Proportion of participants achieving sustained hemoglobin levels ≥ 12 g/dL in the absence of red blood cell transfusions

The number and percentage of patients reaching a fixed threshold ≥ 12 g/dL on three out of four measurements taken at the visits occurring in last six weeks (from Day 126 to Day 168).

The analysis of the secondary endpoint will be a logistic regression and simple proportion to estimate the response probability. The covariates in logistic regression include sex, age (indicator of age ≥ 45 years), an indicator variable of baseline hemoglobin ≥ 8 g/dL and an indicator of transfusion dependence prior to starting study treatment.

This means that the proportion of responders will be derived from the estimated marginal probabilities derived from the model fit as the mean of the individual logistic regression model predictions, together with the 95% confidence intervals, where the standard error will be derived by the bootstrap method ([Steingrímsson et al 2017](#)).

The marginal proportions /response probabilities will be estimated using a logistic regression or simple proportion as for the primary variable ([Section 5.2.2.2](#)).

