2.6.1.2 Transfusion Avoidance

The number and percentage of patients not receiving and not meeting the criteria for administration of packed RBC transfusions in the core treatment period will be summarized overall and by transfusion history during the last 6 months prior to starting study treatment (i.e. transfusion received/not received). The number and percentage of patients not receiving and not meeting the criteria for administration of any RBC transfusion between Day 14 and Day 168 will be summarized overall and by transfusion during the last 6 months prior to start of study treatment (i.e. transfusion received/not received). Time to first packed RBC transfusion from start of study treatment (Day 1) will be plotted using Kaplan Meier curves for overall and by transfusion during the last 6 months prior to start of study treatment (i.e. transfusion received/not received).

For RBC transfusions during the study, the hemoglobin level criterion deemed appropriate by the investigator for requiring the transfusion and signs and symptoms reported prior to receiving transfusion will be summarized. The information will be summarized based on the 'Transfusion-during the study' CRF page.

Transfusion avoidance will be evaluated as the proportion of participants not receiving and not meeting the criteria of administration of RBC transfusion between Day 14 and Day 168, and similarly to the estimation applied to the primary estimand ([Section 2.5.2](#)) by means of standardized marginal proportions. The logistic regression model will include sex, age (indicator of age ≥ 45 years), an indicator variable of baseline hemoglobin ≥ 8 g/dL and an indicator of transfusion dependence.

The marginal proportions /response probabilities will be estimated using a logistic regression or simple proportion as for the primary variable ([Section 5.2.2.2](#)).

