2.13 Interim analysis

No formal interim analyses of efficacy are planned in this study. A data cut-off will be applied and a clinical study report (CSR) will be produced for submission at the time the last patient has completed the core treatment period. An additional CSR will be produced when the last participant has completed the last visit in the extension treatment period, when the final study database has been locked. In addition, if deemed required (e.g. to support regulatory submissions to Health Authorities) interim safety analyses may be produced while the study is still ongoing. If there is an interim lock for safety analyses, [REDACTED]

[REDACTED] The interim report will not consider inferences based on efficacy.

Safety data will be monitored by an independent DMC, and analyses to the effect of this evaluation will be performed during the course of the study with the frequency to be determined in the DMC Charter. Access to a limited number of efficacy measurements by the DMC will be

provided solely for the purpose of evaluating benefit of treatment with iptacopan against any risk. The DMC will function under the the DMC Charter which has been finalized. The Charter includes guidelines for communication concerning safety of participants between the DMC and the sponsor representative to ensure that these are in keeping with the sensitive nature of the open label trial and do not introduce bias.

3 Sample size calculation

The sample size is calculated based on the half-width (the margin of error in the estimate) of a 2-sided 95% confidence interval for the proportion of participants reaching the status of responder (primary endpoint). The proposed sample size of 40 participants is sufficient to achieve a target absolute margin of error not larger than 0.155.

The different scenarios of observed response rate and its 95% confidence intervals are shown in [Table 3-1](#).

Table 3-1 Precision of response rate with N = 40

Sample Size	Observed Response Rate	Unadjusted 95% Confidence Interval
40	30%	(15.8%,44.2%)
40	40%	(24.8%,55.2%)
40	50%	(34.5%, 65.5%)
40	60%	(44.8%,75.2%)

The lower bound of the two-sided 95% confidence interval of the response rate obtained from the primary analysis will be compared to a threshold of 15% and exceeding the threshold is sufficient for demonstration that iptacopan improves hematological response in PNH patients with hemolysis and anemia in the absence of transfusions.

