where $Y_i = 1$ denotes a participant is responder while $Y_i = 0$ denotes a participant is non-responder. Denote the number of imputed dataset to be L and denote θ_j ($j = 1, \dots, L$) to be the proportion of responders for each imputed dataset, simple proportion of responders is the mean of proportion of responders from all the imputed datasets, that is

$$\hat{\theta} = \frac{\sum_{j=1}^L \theta_j}{L}$$

The 95% confidence intervals will be derived by the bootstrap method (Steingrímsson et al 2017). For each bootstrap sample, obtain the simple proportion of responders. Then we will have B estimators, denoted to be $\theta_1^{\{b\}}$, $\theta_2^{\{b\}}$, ..., $\theta_B^{\{b\}}$. The 95% confidence interval is the 2.5% quantile and 97.5% quantile of these bootstrap estimator.

In case of multiple imputation, the simple proportion of responders and the associated two-sided 95% confidence intervals will be obtained by combining multiple imputations with bootstrapping as follows:

- 1) Point estimate will be obtained by averaging across the estimates obtained from each multiple imputed dataset
- 2) The 95% confidence interval will be obtained by bootstrapping each imputed dataset and selecting the 2.5th and 97.5th percentiles of the pooled distribution of bootstrapped parameter estimates as the confidence interval boundaries.

It can be shown that the estimate of the marginal probabilities from logistic regression model and simple estimate of the response probability without any covariates are the same.

From logistic regression,

$$\theta_i = \Pr(Y_i = 1 | S_i, A_i, H_i, T_i) = \frac{\exp [\beta_0 + \beta_1 S_i + \beta_2 A_i + \beta_3 H_i + \beta_4 T_i]}{1 + \exp [\beta_0 + \beta_1 S_i + \beta_2 A_i + \beta_3 H_i + \beta_4 T_i]}$$

The loglikelihood is

$$\text{Loglikelihood} = \sum_{i=1}^N \log[1 - \theta_i] + (\beta_0 + \beta_1 S_i + \beta_2 A_i + \beta_3 H_i + \beta_4 T_i) Y_i$$

Take the derivative of the log likelihood function with respect to β_0 , and let it equal to 0 to obtain

$$\frac{1}{N} \sum_{i=1}^N \theta_i = \frac{1}{N} \sum_{i=1}^N Y_i$$

This indicates that point estimate of the marginal probability from the logistic regression model and the simple response probability without the covariates are the same.

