The 95% confidence intervals from logistic regression model and the simple response probability will be obtained by selecting the 2.5th and 97.5th percentiles of the same pooled distribution of bootstrapped parameter estimates. Therefore, the confidence interval will also be the same for the estimates obtained from the logistic regression model and simple proportion.

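### The percentile-bootstrap 95% CI for the three binary endpoints is adequate at the planned 30–60% rates but overstates precision above about 90%, and has zero width if every participant responds

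*SAP*

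**What the plan says.** SAP 2.5.2.2 estimates the response rate as the mean of logistic-model predictions, with a bootstrap CI. It recognises that "in some imputed datasets or bootstrap samples, all participants are responders/non-responders", treats this as a model-fitting failure, and falls back on the simple proportion: "The 95% CI using simple proportion will also be obtained using the bootstrap method".

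SAP 5.2.2.2 defines the limits. Under multiple imputation they come from "bootstrapping each imputed dataset and selecting the 2.5th and 97.5th percentiles of the pooled distribution of bootstrapped parameter estimates". It then argues that the two routes agree: "Therefore, the confidence interval will also be the same for the estimates obtained from the logistic regression model and simple proportion".

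SAP 2.6.1.1 (Hb ≥12 g/dL) and 2.6.1.2 (transfusion avoidance) carry the method over; the proportions "will be estimated using a logistic regression or simple proportion as for the primary variable". However, SAP 2.6.1.1 also describes the interval as one "where the standard error will be derived by the bootstrap method", and protocol 12.4.2 does the same for the primary endpoint. SAP Section 4, which lists changes from the protocol, mentions only the transfusion-dependence indicator.

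Planning (SAP Section 3, protocol 12.8.1) covers observed rates of 30–60%: "The proposed sample size of 40 participants is sufficient to achieve a target absolute margin of error not larger than 0.155". Protocol 12.4.7 adds subgroups: "The estimation of proportions described above will be further displayed for subgroup categories defined by previous transfusion dependence", among other factors. A Wilson method appears in the SAP only as the last fallback for MAVE and breakthrough-hemolysis rates (2.6.1.7, 2.6.1.8).

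**The concern.** Resampling 40 zero/one outcomes reproduces a Binomial(40, p̂)/40 distribution. As p̂ nears 1 that distribution collapses, and its percentiles no longer reflect the uncertainty about the true rate. At p̂ = 1 every resample equals 1. Switching from the logistic model to the simple proportion cures the convergence failure but leaves the interval as it was, because the SAP itself shows that the two routes give the same interval.

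The error is one-sided and favours the drug: the lower limit is too high. With no control arm, these intervals are what a reader uses to judge how well the response rate is known. Transfusion avoidance is the most exposed endpoint. Every primary responder, and every Hb ≥12 responder, must also be transfusion-free by the same definition, so this proportion cannot be lower than either of the others. It has no planning table.

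**Working it through.** **Inputs.** N=40, two-sided 95% limits and the 15% threshold (SAP 2.5.2.2, Section 3); percentile limits (SAP 5.2.2.2); about 40% of participants with a prior transfusion (protocol Section 3), that is 0.40 × 40 = 16. True rates above 60% are scenarios, not figures from the documents.

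**The plan's own figures.** The planning table is the Wald interval p ± 1.96√(p(1−p)/40).
- At 50%: 1.96√(0.25/40) = 0.155, the stated margin.
- At 30%: 0.30 ± 0.142 = 15.8–44.2%. At 60%: 0.60 ± 0.152 = 44.8–75.2%. Both match.
- The stated 96.4%: 0.15 + 1.96√(0.15×0.85/40) = 0.2607, and (0.40 − 0.2607)/√(0.40×0.60/40) = 1.80, which gives 96.4%. It matches.

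**Intervals at high counts.** The percentile limits are the 2.5% and 97.5% quantiles of Binomial(40, x/40)/40; direct resampling gives the same limits.

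| Responders | Percentile bootstrap | Wilson |
|---|---|---|
| 36/40 | 80.0–97.5% | 77.0–96.0% |
| 37/40 | 82.5–100% | 80.1–97.4% |
| 38/40 | 87.5–100% | 83.5–98.6% |
| 39/40 | 92.5–100% | 87.1–99.6% |
| 40/40 | 100–100% | 91.2–100% |

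At 40/40 the Wilson lower limit is n/(n+1.96²) = 40/43.84 = 91.2%.

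**Exact coverage at N=40.** This is the sum of Binomial(40, p) probabilities over all x whose interval contains p.

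| True rate | Bootstrap | Wilson | Bootstrap lower limit above truth |
|---|---|---|---|
| 0.30 | 96.1% | 94.4% | |
| 0.40 | 96.6% | 96.6% | |
| 0.50 | 96.2% | 96.2% | |
| 0.60 | 96.6% | 96.6% | |
| 0.80 | 96.4% | 92.8% | |
| 0.90 | 91.5% | 94.3% | 8.0% |
| 0.92 | 83.7% | 96.2% | 15.9% |
| 0.925 | 95.3% | 97.2% | 4.4% |
| 0.95 | 86.8% | 95.2% | 12.9% |
| 0.97 | 70.3% | 96.9% | 29.6% |

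The nominal value for the last column is 2.5%. It can be checked by hand. At 0.90 the lower limit is too high at 39/40 and 40/40: 40×0.9³⁹×0.1 + 0.9⁴⁰ = 0.0657 + 0.0148 = 0.0805. At 0.95 only 40/40 fails on that side: 0.95⁴⁰ = 0.129. At 0.97: 0.97⁴⁰ = 0.296.

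Coverage is a sawtooth, so averages matter more than single points:
- Rates 0.30–0.60: bootstrap mean 94.2%, minimum 91.9%.
- Rates 0.90–0.95: bootstrap mean 88.7%, Wilson 95.8%.
- Rates 0.90–0.99: bootstrap mean 78.8%, Wilson 95.6% (Wilson minimum 89.7%).

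**Standard-error reading.** An interval built from a bootstrap standard error is close to Wald. It covers 86.8% at 0.95 and also has zero width at 40/40, so the other wording does not help.

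**Subgroup of n=16, if the same interval is used there.** Bootstrap coverage is 85.2% at 0.80, 92.0% at 0.85 and 79.8% at 0.90; Wilson gives 94.5%, 97.7% and 93.2%. P(16/16) at 0.90 is 0.9¹⁶ = 0.19, and the interval is then 100–100%, against 80.6–100% for Wilson (16/19.84 = 80.6%).

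**The case against.** The strongest reply is that nothing the plan decides is affected. The only formal criterion is the 15% threshold, which every method clears easily at high rates, and no success criterion attaches to the two secondary proportions. The planned rates are 30–60%, where the method works. A 100–100% interval needs all 40 to respond in effectively every imputed dataset, and a withdrawal after stopping iptacopan, imputed from baseline hemoglobin, would usually count as a non-response. All of that is correct, and it limits the severity.

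Three further points stand in part.
- Coverage is not monotone: 95.3% at 0.925 sits beside 83.7% at 0.92. At 37/40 the two widths are nearly equal (17.5 against 17.3 points). Even there the bootstrap lower limit is 2.4 points higher, and the averages show that the shortfall is systematic.
- The SAP text on subgroups is redacted, so the interval used there is unknown. The n=16 figures are conditional on it being the same one.
- SAP 2.6.1.1 ends by referring to 5.2.2.2, which partly resolves the standard-error wording. The difference from protocol 12.4.2 remains unlisted in Section 4.

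Wilson is not uniformly better: at 0.80 it covers 92.8% against 96.4% for the bootstrap. The coverage figures here are for complete data; coverage of the multiple-imputation form has not been computed.

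The reply does not remove the defect. The SAP foresees all-responder datasets and still treats the resulting bootstrap interval as valid.

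**Conclusion.** The concern holds and should be fixed. At the planned rates the interval is sound. From about 90% upward it is anti-conservative, with mean coverage of 78.8% over 0.90–0.99 and lower limits about 2 to 5 points above Wilson at 36–39/40. At 40/40 it has no width. The two descriptions of the interval, percentile and standard error, also need to become one.

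This rests on N=40, complete data for the coverage figures, and an assumed true rate near or above 90%, which the documents neither predict nor rule out. The 15% decision is not in question.

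**What to change.** In SAP 5.2.2.2, pre-specify one interval for all three binary endpoints and their subgroups, whatever the missing-data pattern: a Wilson score interval in multiple-imputation form.

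Let p̄ be the mean of the L imputed proportions and V_B = (1+1/L) × the between-imputation variance. The limits are the two roots in p of (p̄ − p)² = c²[p(1−p)/n + V_B], cut at 0 and 1. Use c = 1.96 if V_B = 0, otherwise the t quantile with Rubin's degrees of freedom. With nothing imputed this is ordinary Wilson.

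Example: 39 observed responders plus one participant imputed as a responder in 50 of 100 datasets.
- p̄ = (50×1 + 50×0.975)/100 = 0.9875.
- Between-imputation variance = 0.0125² × 100/99 = 0.0001578, so V_B = 1.01 × 0.0001578 = 0.0001594.
- Mean within-imputation variance = 0.5 × 0.975 × 0.025/40 = 0.0003047, so df = 99 × (1 + 0.0003047/0.0001594)² ≈ 839 and c = 1.963.
- The roots are 0.886 and 1.004, so the interval is 88.6–100%, against 92.5–100% by the SAP method.

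Align the wording in SAP 2.6.1.1 and record the departure from protocol 12.4.2 in SAP Section 4. The bootstrap interval can stay as supportive.

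The cost is a SAP amendment, a closed-form calculation, and somewhat wider intervals at most high counts. With complete data and the ≥15% rule of SAP 2.5.2.2, the success cut-off stays at 11/40. The percentile lower limit there is exactly 15.0% and Wilson's is 16.1%; 10/40 fails both (12.5% and 14.2%). P(X≥11) is 2.99% at a true rate of 15% and 96.5% at 40%, close to the stated 96.4%.
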